8.2.7. Visit 11: Week 24 (+/- 7 days) - End of study visit

At the end of the 24-week treatment and follow-up period, patients undergo an end of study visit evaluation. This visit occurs 3 weeks after the 7th course of study drug at a dose of 1 g/kg.

In the event of premature discontinuation from the study drug or patient withdrawal from the study, an end of study visit is performed within 7 days.

The end of study assessment should be performed before any other treatment including Igs is administered.

The reason for premature study drug discontinuation / study withdrawal should be accurately assessed and entered into the eCRF.

The following study procedures will be carried out:

- Complete physical examination.
- Biometric information: weight.
- Vital signs: temperature, heart rate, systolic and diastolic blood pressure.
- Neurological status assessment:
 - INCAT disability score (adjusted INCAT disability score will be deduced from reported values).
 - Patient and Investigator CGI-S, CGI-E and CGI-I.
 - MRC sum score.
 - Rasch-modified MRC sum score.
 - R-ODS.
 - Grip strength with Martin vigorimeter in both hands.
- Biological tests in local laboratory:
 - Haematology:

- Complete blood count + differentials, Hb, MCV, platelets count.
- Haptoglobin.
- Reticulocytes, direct Coombs test
- Biochemistry:
 - Creatininemia, glomerular filtration rate according to MDRD.
 - LDH.
 - Total and free bilirubin (total bilirubin in all patients; if total bilirubin > ULN, free bilirubin will be assessed from the same blood sample, as total bilirubin).
 - AST, ALT, ALP, γ GT.
 - Total serum protein level.
 - C3 and C4 antigens.
 - Serum total IgG trough levels.
- HBs Ag, anti HBs & anti HBc Ab, HIV, HCV tests.
- Serum reference sample for long term storage.
- Urine protein reagent strip test [to be performed before study drug administration in patients who at screening tested for urine protein reagent strip result "1 cross 1 (+) and/or had GFR in the range of 60-80 mL/min/1.73m²]:

If urine protein reagent strip test result = Negative or Trace	Action: No further urine test required
If urine protein reagent strip test result = 1 cross (1 +) or more	Action: Assess either AER or PER from a 24h-urine collection sampled at least 7 days after the end of the previous study drug course or assess ACR or PCR from a spot urine sample immediately following the urine protein reagent strip test (i.e. urine obtained before study drug administration).

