8.3. At any course

In case of suspected clinical venous thrombosis: D-Dimers testing will be performed.

In case of suspected haemolysis based on biological tests (Hb, haptoglobin, LDH, total and free bilirubin levels (total bilirubin in all patients; if total bilirubin > ULN, free bilirubin will be assessed from the same blood sample, as total bilirubin)): Reticulocytes and direct Coombs test will be performed.

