2.6. Study Plan Table

	Screening	First study drug administration	Day 4 after last infusion at V2	Week 3	Week 6	Week 9	Week 12	Week 15	Week 18	Week 21	End of study visit
	VISIT 1	VISIT 2	VISIT 3	VISIT 4	VISIT 5	VISIT 6	VISIT 7	VISIT 8	VISIT 9	VISIT 10	VISIT 11
Informed consent (before any procedure of study)	X										
Inclusion/exclusion criteria verification	X	X									
Demographics & Medical history	X										
Safety											
Adverse events assessment	X	X	X	X	X	X	X	X	X	X	X
Phone call 4 days (+/- 1 day) after study drug administration				X	X	X	X	X	X	X	
Concomitant medications	X	X	X	X	X	X	X	X	X	X	X
Patient diary (delivery and verification)	X	X	X	X	X	X	X	X	X	X	X
Clinical assessments / Before study drug administration											
Complete physical examination	X	X	X								X
Clinical examination focused on arterial or venous thromboembolic signs				X	X	X	X	X	X	X	
Weight, Body temperature, heart rate, arterial blood pressure (systolic and diastolic)	X	X	X	X	X	X	X	X	X	X	X
Efficacy assessments / Before study drug administration											
INCAT disability score	X	X		X	X	X	X	X	X	X	X
MRC sum-score, Rash modified MRC sum-score R-ODS Grip Strength (both hands)		X					X				X
Patient and Investigator: CGI (Severity)		X					X				X
Patient and Investigator: CGI (Efficacy), CGI (Improvement)							X				X

Biological test Local lab / Before study drug administration	VISIT 1	VISIT 2	VISIT 3	VISIT 4	VISIT 5	VISIT 6	VISIT 7	VISIT 8	VISIT 9	VISIT 10	VISIT 11
Serum Total IgG trough levels		X		X	X	X	X	X	X	X	X
HbA1c (only for patients with a known history of diabetes mellitus), serum IgA levels	X										
Urine protein reagent strip test	X ^a		X ^b	X ^b	X ^b	X ^b	X ^b	X ^b	X ^b	X ^b	X ^b
Urine Pregnancy test for female of child bearing potential	X										X
C3 and C4 antigens		X	X	X							X
Anti HBs & anti HBc Ab, HBs Ag tests, HIV and HCV tests	X										X
Complete blood count and differentials, Hemoglobin, Mean corpuscular volume, platelet count, haptoglobin, LDH	X		X	X	X	X	X	X	X	X	X
Reticulocytes, direct Coombs test, total serum protein level	X										X
AST, ALT, γ GT, ALP	X										X
Creatininemia, GFR ^c , total and free bilirubin ^d	X		X	X	X	X	X	X	X	X	X
Serum reference sample for long term storage		X									X
Biological test Local lab in case of suspected clinical thrombosis											
D-Dimers		X	X	X	X	X	X	X	X	X	X
Biological test Local lab in case of suspected hemolysis											
Reticulocytes, direct Coombs test		X	X	X	X	X	X	X	X	X	X

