A scatter plot of the values at the EOS assessment as well as the minimum and maximum values of each patient during the treatment follow-up against the values at baseline will be prepared for each parameter. The first diagonal will be displayed by a dotted line.

4.7.3. 1.2. Course and infusion level analyses

Descriptive statistics of laboratory parameters at screening, before and 96h after the 1st IMP course, before the start of each subsequent course and at the EOS assessment will be provided for laboratory parameters as well as for the clinical assessment. The change from before first IMP course to 96h after the 1st IMP course as well as to before subsequent courses will be presented as well as the minimum and maximum values of each patient during the complete treatment follow-up. The complete treatment follow-up of maximum and minimum presentations includes all post-baseline assessments, along with any unscheduled assessment results which do not contribute to by visit descriptive summaries. Similarly, shift tables for the clinical assessment will be produced showing the change from before the first IMP course to 96h after the 1st IMP course as well as to before subsequent courses.

A graphical display of the evolution of each laboratory parameter by course will be presented with connected box-and-whisker plots. The number of observations at each visit will be displayed in the graph.

Detection of hemolysis will be evaluated at course level. The number and percentage of course with hemolysis will be displayed by subgroup and overall in accordance with the IVIg-associated hemolysis criteria published by Health Canada ([Health Canada 2009](#)), adapted to the study as follows:

- Drop in hemoglobin by at least 1 g/dL compared to baseline and
- At least one of the two criteria below are met
 - Positive direct Coombs test
 - At least 2 of the following criteria are met (in absence of negative direct Coombs test):
 - * Reticulocyte count increased by at least $50 \times 10^9/L$ compared to baseline
 - * LDH increased by at least 20% compared to baseline
 - * Haptoglobin value is lower than the lower limit of normal (LLN)
 - * Free bilirubin (or total bilirubin if the free bilirubin is not documented) increased compared to baseline and value is greater than the upper limit of normal (ULN)

In the following situations the courses will be excluded from the analysis:

Criterion for hemoglobin value cannot be evaluated/calculated

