Criterion for hemoglobin is evaluable, direct Coombs test neither positive or negative (missing or not-done) and

- 3 or 4 out of 4 criteria (Reticulocytes, LDH, Haptoglobin, free/total bilirubin) cannot be evaluated/calculated or
- 1 or 2 out of 4 criteria (Reticulocytes, LDH, Haptoglobin, free/total bilirubin) cannot be evaluated/calculated and less than two of the remaining criteria are met

A listing of all hemoglobin, reticulocytes, LDH, haptoglobin and bilirubin values will be provided for patients with at least one blood sample for which the aforementioned criteria for hemolysis is met. A listing of the excluded courses will be also given.

All abnormalities, clinically significant or not, will be listed. Pregnancy status and test results will also be listed, including the method of contraception used (if any).

4.7.3. 2. *Vital signs*

Vital signs parameters including systolic and diastolic blood pressure (mmHg), heart rate (bpm), weight, and body temperature (°C) (calculated value according to the way the temperature was measured) will be summarized.

4.7.3. 2.1. Patient level analyses

Descriptive statistics of vital sign values will be presented for the following time points:

- a) Screening
- b) Before the 1st IMP infusion
- c) 30-45 min and 60-75 min after the start of the first infusion
- d) 30-45 min after the end of the first infusion
- e) 96h after the end of the 1st course
- f) EOS

Change from time point b) will be presented for time points c) to e). The minimum and maximum of each parameter during the patient's complete treatment follow-up will be presented. The complete treatment follow-up of maximum and minimum presentations includes all post-baseline assessments, along with unscheduled assessment results which do not contribute to by visit and by timepoint descriptive summaries.

A scatter plot of the values at the end of study assessment as well as the minimum and maximum values of each patient during the treatment follow-up against the values at baseline will be prepared for each parameter. The first diagonal will be displayed by a dotted line.

4.7.3. 2.2. Course and infusion level analyses

Descriptive statistics of vital sign values will be presented at the following time points:

- a) Before the start of the course (only first infusion of a course)
- b) 30-45 min and 60-75 min after the start of the infusion
- c) 30-45 min after the end of the infusion

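### The haemolysis table drops courses already known to be negative, because its exclusion asks whether haemoglobin is evaluable and not whether it fell

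*SAP*

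**What the plan says.** SAP Section 4.7.3.1.2 defines haemolysis per course. The first, mandatory element is "Drop in hemoglobin by at least 1 g/dL compared to baseline and" at least one of two further conditions: a positive direct Coombs test, or, where Coombs is not negative, at least two of four markers (reticulocytes, LDH, haptoglobin, bilirubin). The summary is a count and a proportion: "The number and percentage of course with hemolysis will be displayed by subgroup and overall".

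Two exclusions follow, introduced by "In the following situations the courses will be excluded from the analysis". The first removes courses whose haemoglobin criterion cannot be evaluated. The second begins "Criterion for hemoglobin is evaluable, direct Coombs test neither positive or negative (missing or not-done) and" then requires either that three or four markers cannot be evaluated, or that one or two "cannot be evaluated/calculated and less than two of the remaining criteria are met". Two listings are also planned: laboratory values for patients with a sample meeting the criteria, and the excluded courses.

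On sampling, the SAP study plan table (Section 2.6) has a row "Reticulocytes, direct Coombs test, total serum protein level" marked only at Visits 1 and 11. Protocol Section 8.3 adds reticulocytes and Coombs at other times only on suspicion: "In case of suspected haemolysis based on biological tests (Hb, haptoglobin, LDH, total and free bilirubin levels". Patients who stop early also get the EOS tests, since "an end of study visit is performed within 7 days" (Protocol Section 8.2.7).

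**The concern.** Because the haemoglobin drop is mandatory, a course with evaluable haemoglobin and no drop is negative whatever the other tests show. The second exclusion does not use that information. It applies to every course with evaluable haemoglobin, drop or no drop, and no other sentence brings the no-drop courses back.

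The count of remaining markers separates established cases from undetermined courses only once a drop has occurred. Applied to no-drop courses it works backwards: those with two or three abnormal markers stay in, and those with none or one go out.

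At stake is the percentage in a table the SAP added because the protocol had no suitable haemolysis analysis (SAP Section 4.10.2). Its denominator would lack many courses whose status is known.

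**Working it through.** The plan states no haemolysis figure, so there is nothing to reproduce. The check has a logical part, which needs no assumed rates, and a hypothetical size.

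**1. All data patterns for one course.** Haemoglobin (drop, no drop, not evaluable) × Coombs (positive, negative, missing) × four markers (met, not met, missing) gives 3 × 3 × 3⁴ = 729 patterns.

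- Excluded as written: 329.
- Excluded if the second exclusion requires the drop to be met: 286.
- Difference: 43, all with no drop and Coombs missing. By number of missing markers: one, 4 × 4 = 16; two, 6 × 3 = 18; three, 4 × 2 = 8; four, 1.
- Excluded patterns that meet the definition: 0 under either rule. None of the 43 can become a case however its missing values are filled in.

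**2. The routine pattern.** Coombs and reticulocytes not done; LDH, haptoglobin and bilirubin available.

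| Markers met | No drop | Drop |
|---|---|---|
| 0 or 1 | excluded | excluded |
| 2 or 3 | kept, non-case | kept, case |

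**3. Direction.** Let k be the retained cases, R the retained courses and E the excluded no-drop courses. The plan reports k/R; with the exclusion limited to drop courses it is k/(R + E). If k ≥ 1 and E ≥ 1, the first is larger. If k = 0, both are 0%.

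**4. Exposure.** 42 patients × 8 courses = 336 planned courses. If the EOS sample is attributed to the eighth course, 42 courses have Coombs and reticulocytes scheduled and 42 × 7 = 294 (87.5%) do not.

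**5. Hypothetical size.** None of these rates is in the documents. Assume:

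- h = 1, 2 or 5% of courses meet the definition, all retained;
- s = 0, 5, 10 or 20% of the other courses 1–7 are tested on suspicion;
- each of LDH, haptoglobin and bilirubin is met with probability m = 5, 10 or 20%, independently, so P₂ = 3m²(1−m) + m³ is the chance that at least two are met;
- d = 10, 25 or 40% have a haemoglobin drop.

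As written: 336h + 42(1−h) + 294(1−h)[s + (1−s)P₂(1−d)], giving 46.2 to 133.5 courses.

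Limited to drop courses: 336h + 42(1−h) + 294(1−h)[(1−d) + ds], giving 219.6 to 313.7 courses.

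The loss is 120.1 to 260.1 courses and the ratio of percentages 1.95 to 6.55. Mid-range example (h 2%, s 10%, m 10%, d 25%; P₂ = 0.028):

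- as written, 6.72 + 41.16 + 288.12 × 0.1189 = 82.1 courses, so 6.72/82.1 = 8.2%;
- limited to drop courses, 6.72 + 41.16 + 288.12 × 0.775 = 271.2 courses, so 6.72/271.2 = 2.5%.

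If testing is more frequent after a drop (20, 50 or 80%) than without one (0 to 20%), as Protocol Section 8.3 suggests, the ratio is 1.62 to 5.94.

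**6. Against the true rate.** If a share c of true cases is captured, reported/true = 336c divided by the as-written denominator, with 336hc in place of 336h. With c = 1 this is 2.52 to 7.27; with c = 0.25 it is 0.69 to 1.92. The direction can reverse.

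**The case against.** The strongest reply is about consequence. The table is descriptive, in a single-arm trial, with no haemolysis test, threshold or stopping rule. The error hides no case, and relative to the amended rule it overstates a harm. The two listings show the flagged patients and the excluded courses, so the percentage could be recalculated without new data. All of this stands and sets the severity. It does not correct the planned percentage, and nothing requires the excluded-course listing to separate known negatives from undetermined courses.

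The size is also open to attack, rightly. The assumed rates do not always agree with each other. The 6.55 ratio arises at h 1%, s 0, m 5%, d 10%, where those marker and drop rates imply about 294 × 0.10 × 0.00725 = 0.2 cases in courses 1–7, against 336 × 0.01 = 3.4 assumed overall. At m 20%, d 40% they imply 294 × 0.40 × 0.104 = 12.2. The SAP also does not say which sample belongs to which course, so the 294/42 split is an assumption.

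A reader might infer that the amended percentage would cover all determinable courses. It would not quite. Courses with haemoglobin missing and Coombs negative are definite non-cases but stay excluded (81 patterns). Courses with a drop, Coombs missing and all four markers known with fewer than two met stay in as non-cases, although a positive Coombs would make them cases (5 patterns).

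**Conclusion.** The point holds as a wording error with a definite direction relative to one comparator. The second exclusion removes definite non-cases and leaves the case count alone. If at least one retained course is a case and at least one such no-drop course is removed, the planned percentage is too high relative to the same rule restricted to courses with a drop. The sampling schedule makes such removals routine, since an unsuspected course without an EOS sample normally has neither Coombs nor reticulocytes.

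A reader might go further and infer that the table overstates the true haemolysis rate. The documents do not support that: drop courses with undetermined markers are also excluded, some may be true cases, and the direction then depends on how many cases are captured.

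The exposure ceiling of 294 of 336 courses rests on full completion of the planned courses and on attributing the EOS sample to the eighth course. The range of roughly 1.6- to 6.6-fold is an illustration from assumed rates, not an estimate. Confidence is high in the logic and low in the size. Severity is low: the primary endpoint and all hypothesis tests are untouched.

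**What to change.** In SAP Section 4.7.3.1.2, state that a course whose haemoglobin criterion is evaluable and not met is classified as no haemolysis, and that the exclusion based on Coombs and the markers applies only to courses in which the haemoglobin drop is met. Beside the percentage, report the number of drop courses excluded as undetermined.

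The cost is one or two sentences, one extra count and minor programming, with no new data. The limit is that undetermined drop courses remain outside the denominator: 294(1−h)d(1−s), or about 22 to 116 courses on the assumed rates with equal testing. The amended figure would still not be the true haemolysis rate, and the extra count lets the reader see how far it might be from it.

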4.8. Pharmacokinetics

Not Applicable.

4.9. Exploratory analyses

The following exploratory endpoints will be analyzed and summarised by visit using FAS for absolute value and change from baseline.

- Anti-CNTN1 and anti-NF155 antibodies titers at EOS visit
- FcγRIIB B cells marker levels at visits V2, V3 and V4
- BAFF and complement components (C3 and C4 antigens, CH50) at visits V2, V3, V4 and EOS visit
- Serum total IgG trough levels before each course

In order to explore the relationship between the biomarkers and clinical response at EOS a univariate logistic regression model will be applied. Each biomarker will be studied separately at each visit. The by visit univariate model will use the biomarker change from baseline (quantitative) as a single exploratory variable, with the clinical response at EOS being the dependent variable.

To explore the relationship of the total IgG trough level and the adjusted INCAT disability score a linear mixed model will be used using the patient as random factor. A scatterplot will show all values and the estimated regression line and its 95% confidence band.

A non-parametric regression method will also be applied (e.g. LOESS, splines or generalised additive models) in order to explore departures from linearity. The result of the estimated regression line will also be shown in a scatterplot together with the 95% confidence band. Similar exploration of the relationship between the biomarkers and other clinical response variables will be conducted as needed using generalized linear mixed models.

A listing of the biomarker data will be produced. In addition, a listing of patients included in the ultrasonography ancillary study will be provided. However, no statistical analysis will be done (see section [4.10.3](#)). The listing will include information on the consent date for the ancillary study and whether data were collected (Yes/No).

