1.4.2. Immunological background and research of biomarkers

The pathogenesis of CIDP is not fully understood. T cells, B cells, macrophages, cytokines and chemokines, autoantibodies and complement are the main effectors involved in the pathogenesis of CIDP and are therefore the main target of therapies. Immune cells and soluble mediators are

regulated by IVIg and this regulation is correlated in many instances with IVIg response. Numerous biomarkers have been proposed in CIDP but none seems to predict the response to IVIg accurately. This trial gives the opportunity to assess specific biomarkers, their modulation by IVIg treatment and their correlation with clinical response.

IVIg seems to work by a direct competition and quantitative blockade of autoantibody action by different mechanisms.

In 2013 [name] highlighted IgG4 anti-contactin1 (CNTN1) and anti-neurofascin (NF155) autoantibodies as poor prognostic factors after IVIg therapy: in her series, the presence of at least one of these autoantibodies identified a lack of response to IVIg [15]. Anti-CNTN1 and anti-NF155 antibodies were associated to small subgroups of CIDP patients with specific phenotypic features.

The concept of an aberrant B cell response as a pathogenic part of CIDP is widely accepted. IgG mediated effector functions require the interaction with their Fc γ R on effector cells. The type II Fc γ RIIB (CD32B) is the only inhibitory Fc γ R and is expressed on circulating monocytes and B cells. On B cells, signalling through this receptor inhibits transformation of B cells into antibody secreting plasma cells [16]. Recent works has shown that this receptor is modulated by IVIg in CIDP patients [17] [18] [19].

The immune status of patients as well as their modulation by a high dose of IVIg (2g/kg) will be documented by monitoring the expression of the Fc γ RIIB B cell marker in blood.

Other soluble biomarkers such as (BAFF) contribute to B-cell homeostasis and autoantibody production [20].

Complement components have been shown to be modulated by IVIg [21] [22]. Scavenging of complement fragments is a mechanism believed to be important in the efficacy of IVIg. Binding of IgG molecules to potentially harmful complement fragments (C3b, C4b) blocks deposition of these fragments onto their target and the formation of amplification convertases, decreasing activation of C5 and deposition of the C5b-C9 membrane attack complex.

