2.3. Exploratory objectives

- To assess a potential relationship between serum total IgG trough levels, biomarkers levels and clinical response – as assessed by neurological scales – in patients with CIDP.
- To assess a potential relationship between USG coupled to neurophysiology analysis of nerves and clinical response – as assessed by neurological scales – in patients with CIDP (ancillary study in Italy).

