3.2.4. Exploratory endpoints

The following exploratory endpoints will be considered:

Biomarker study:

- Anti-CNTN1 and anti-NF155 antibodies titers at screening and EOS visit.
- Fc γ RIIB B cells marker levels at visits V2, V3 and V4.
- B cell activating factor (BAFF) and Complement components (C3 and C4 antigens, CH50) at visits V2, V3, V4 and EOS visit.
- Serum total IgG trough levels at each visit, within 24 hours prior to study drug administration.

Ancillary study in Italian sites only:

- Change from baseline to EOS visit in nerve conduction velocities, distal latencies, amplitude of the negative phase of compound muscle action potentials and F wave for the following peripheral nerves: median nerve, ulnar nerve and deep fibular nerve (F wave assessed on ulnar nerve only).
- Change from baseline to EOS visit in nerve maximal/minimal cross section area (CSA), intra-nerve and inter-nerve variability and USG immune-related classification (see Section [1.4.4](#). Peripheral nerve ultrasonography), in the following peripheral nerves: median nerve, ulnar nerve, fibular nerve and sural nerve.

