12.11. Exploratory Analysis

The following exploratory endpoints will be analysed:

- Anti-CNTN1 and anti-NF155 antibodies titers at screening and EOS visit.
- FcγRIIB B cells marker levels at visits V2, V3 and V4.
- BAFF and complement components (C3 and C4 antigens, CH50) at visits V2, V3, V4 and EOS visit.
- Serum total IgG trough levels before each study drug administration.
- Change from baseline to EOS visit in nerve conduction velocities, distal latencies, amplitude of the negative phase of compound muscle action potentials and F wave for the following peripheral nerves: median nerve, ulnar nerve and deep fibular nerve (F wave assessed on ulnar nerve only).
- Change from baseline to EOS visit in nerve maximal/minimal cross section area (CSA), intra-nerve and inter-nerve variability and ultrasound (USG) immune-related classification (see Section [1.4.4](#) Peripheral nerve ultrasonography) in the following peripheral nerves: median nerve, ulnar nerve, fibular nerve and sural nerve.

All exploratory variables will be described in summary tables. The relationship between these variables and clinical response will be explored and detailed in the SAP.

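### SAP 4.9 pre-specifies no analysis of response by screening anti-CNTN1/anti-NF155 status, although the protocol measures these antibodies as markers of lack of response to IVIg

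*SAP*

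**What the plan says.** Protocol 1.4.2 gives a reason specific to these two antibodies. It describes them as "autoantibodies as poor prognostic factors after IVIg therapy" and reports that, in the series it cites, "the presence of at least one of these autoantibodies identified a lack of response to IVIg". The same section gives a wider purpose for the whole biomarker panel: "This trial gives the opportunity to assess specific biomarkers, their modulation by IVIg treatment and their correlation with clinical response".

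The exploratory objective in protocol 2.3 is "To assess a potential relationship between serum total IgG trough levels, biomarkers levels and clinical response". The endpoint in protocol 3.2.4, repeated in 12.11, is "Anti-CNTN1 and anti-NF155 antibodies titers at screening and EOS visit". Protocol 12.11 then hands over the method: "The relationship between these variables and clinical response will be explored and detailed in the SAP".

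SAP 2.5.4 keeps both time points. SAP 4.9, which sets out what will be analysed, lists "Anti-CNTN1 and anti-NF155 antibodies titers at EOS visit". It relates biomarkers to response at EOS through a logistic regression fitted separately for each biomarker and visit, and defines the predictor thus: "The by visit univariate model will use the biomarker change from baseline (quantitative) as a single exploratory variable".

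**The concern.** The protocol's reason for measuring the antibodies is about status: whether patients who carry at least one of them fail to respond. The SAP's model asks something else: whether patients whose titre moved during the study responded differently from those whose titre did not. If the SAP is followed as written, the study report could describe the relationship between these antibodies and response without comparing seropositive with seronegative patients.

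The screening samples are already planned, so the loss would come from the analysis plan alone. A table added after results are known would carry less weight than one fixed in advance, particularly when it may rest on a handful of patients.

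**Working it through.** **1. What the protocol asks against what the SAP specifies**

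| Item | Protocol | SAP |
|---|---|---|
| Reason or target | Presence as a marker of lack of response (1.4.2); biomarker levels and response (2.3) | Change from baseline and response (4.9) |
| Antibody time points | Screening and EOS (3.2.4, 12.11) | Screening and EOS (2.5.4); EOS only (4.9) |
| Relation of screening titre to response | Left to the SAP (12.11) | None specified |
| Departure recorded | – | Not in 4.10 |

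**2. Does another part of the SAP fill the gap?**

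- SAP 3.4: subgroups are Ig-naïve and Ig-pretreated, with age, sex, race and BMI added for adverse events. None is by antibody status.
- SAP 4.3: the baseline characteristics include no antibody result.
- SAP 5.7: no positivity variable or cut-off is derived.
- SAP 4.9: the linear mixed model concerns total IgG trough and adjusted INCAT. The closing provision for generalized linear mixed models is optional, is aimed at response variables other than EOS response, and names no baseline predictor.

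**3. Can the change stand in for status?**

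The study plan (SAP 2.6) samples the antibodies at screening and EOS only, so each patient has one value per antibody:

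change = EOS titre − screening titre.

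- Seronegative throughout: about 0 − 0 = 0.
- Persistently seropositive at titre T: about T − T = 0.
- Seropositive with a falling titre: below 0.

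The first two groups are the ones the hypothesis contrasts, and the predictor places them together. The value also becomes available only at the visit where response is judged, so it cannot serve as a prognostic factor.

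**4. How much could the missing table show?**

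The plan states no figure for this analysis. The denominator used here is the plan's 38 evaluable patients, which reproduces: with a null rate of 33.3%, success needs at least 19 of 38 responders, the exact one-sided alpha is 0.0244, and power at 60% is 0.922.

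The documents give no prevalence, only that the antibodies go with small subgroups. Assumed values:

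| Assumed prevalence p | Expected seropositive, 38 × p | Chance of none, (1 − p)^38 |
|---|---|---|
| 2% | 0.76 | 46% |
| 5% | 1.9 | 14% |
| 10% | 3.8 | 2% |

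Suppose further that no seropositive patient responds and about 60% of the others do. The exact upper 95% limit for 0/k is 1 − 0.025^(1/k). The two-sided Fisher p is, for k = 3, C(17,3)/C(38,3) = 680/8436 = 0.081, and similarly for the other rows:

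| Seropositive k | Others responding | Exact 95% CI for 0/k | Fisher p |
|---|---|---|---|
| 1 | 22/37 | 0 to 97.5% | 0.42 |
| 2 | 22/36 | 0 to 84.2% | 0.17 |
| 3 | 21/35 | 0 to 70.8% | 0.081 |
| 4 | 20/34 | 0 to 60.2% | 0.041 |

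The p-values move with the assumed response. With k = 3, 23/35 responders among the others gives C(15,3)/C(38,3) = 455/8436 = 0.054, and 19/35 gives 2 × C(19,3)/C(38,3) = 2 × 969/8436 = 0.23. The table would describe the data, with wide intervals; it would not be a confirmatory test.

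**The case against.** The strongest reply is that little is lost. SAP 3.4 treats exploratory analyses as purely descriptive. SAP 4.9 and 5.1 provide listings of the biomarker data and of all patient data, and SAP 4.9 leaves room for further modelling. With one to four seropositive patients, a reader could match screening status to response by hand. Much of this stands. One might infer that the study can never relate baseline status to response, and the documents do not support that; what is missing is a pre-specified analysis. Nor is the screening titre discarded, because the EOS change cannot be computed without it.

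A second reply is that change from baseline is a proper variable. This stands for the modulation aim in protocol 1.4.2. That section justifies FcγRIIB, BAFF and complement by their modulation under IVIg, so requiring baseline terms for those markers would be a preference and not a correction. For the two antibodies, the reason given is their presence. Protocol 1.4.2 does not say in terms that presence is judged before treatment, but a prognostic factor for response to therapy is most naturally read that way, and screening is the only pre-treatment sample.

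Two further inferences should be resisted. One is that the planned logistic model could not be fitted; that needs an identical change in every patient, which nothing in the documents indicates. The other is that EOS titres are invalid because of passively transferred antibody. The warning in protocol 9.2.1 is general, its example is red-cell antibodies, and it does not mention these assays.

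**Conclusion.** The point holds in a limited form. SAP 4.9 pre-specifies no analysis relating screening anti-CNTN1/anti-NF155 status or titre to response, and its one biomarker-response model cannot separate seronegative from persistently seropositive patients. The protocol's stated reason for measuring these antibodies therefore goes untested if the SAP is followed as written, and SAP 4.10 is silent on the departure.

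This follows from comparing the texts and does not depend on the illustrative figures. Those rest on assumed prevalence and response rates and show only that the estimate would be imprecise and that there might be no seropositive patient at all. The consequence stays within one exploratory objective. The correction is worth making because it answers the trial's own question from samples already planned.

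**What to change.** In SAP 4.9:

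- Restore the screening titre of both antibodies to the summarised variables.
- Define positivity by the central laboratory's assay cut-off, fixed before database lock. The documents refer to titres and give no cut-off.
- Tabulate the EOS responder rate by screening status (positive for at least one antibody against negative for both) with exact 95% confidence intervals, labelled descriptive. If no patient is positive, report that.
- Keep the change-from-baseline model for the modulation aim.

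Record the addition in SAP 4.10. Baseline terms for BAFF, complement and FcγRIIB are optional.

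The cost is a few lines of SAP text and one more exploratory table. No new samples or visits are needed. The drawback is one more imprecise estimate, which the wide intervals will make plain.
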